#### Primary Endpoint

1. Uterine tone score as recorded at 10 minutes following the administration of the second-line uterotonic.

#### Secondary Endpoints

1. Uterine tone score recorded at 5 minutes following the administration of the second-line uterotonic.
2. Need for an additional uterotonic agent after the study drug
3. Number of units of blood products transfused ( $t_0$  = time of delivery;  $t_{final}$  = 24 hours after delivery)
4. Need for a surgical or radiologic intervention to control bleeding
5. Quantitative intrapartum blood loss
6. Pre- vs post-delivery hematocrit values
7. Maternal morbidity: vasopressor requirement or hypovolemic shock, admission to the intensive care unit postpartum, mechanical ventilation, hypertensive emergency, myocardial ischemia, acute kidney injury, acute lung injury or circulatory overload from blood transfusion, allergic reaction deemed the result of blood transfusion, hypovolemic shock, or vasopressor requirement.
8. Length of postoperative hospital stay

9. Medication side effects within 2 hrs postpartum: nausea, vomiting or diarrhea, abdominal pain, shortness of breath, headache, blurred vision, anxiety, chest pain, sweating, palpitations

For studies involving treatment or diagnosis, provide information about standard of care at Partners (e.g., BWH, MGH) and indicate how the study procedures differ from standard care. Provide information on available alternative treatments, procedures, or methods of diagnosis.

All patients undergoing a C/S delivery at the Brigham and Women's Hospital (BWH) have a peripheral IV and baseline laboratory work on admission to the labor and delivery floor. The standard of care at BWH for women undergoing C/S includes spinal anesthesia with bupivacaine, fentanyl, and morphine, as will be used in this study unless contraindicated. The overall anesthetic management of a patient in the operating room will be at the discretion of the anesthesia attending physician, including crystalloid fluid administered, anti-emetic medication, analgesic medication and vasopressors used. Blood products transfused will be at the discretion of the attending physicians.

At the time of C/S and clamping of the umbilical cord, a standard infusion of oxytocin 30U/500mL is begun at a rate of 15-30U/hr. If uterine tone is perceived to be inadequate, this rate may be increased and the obstetrician may attempt maneuvers to improve uterine tone. Additionally, at this time a second-line uterotonic is typically requested.

The choice of whether to give methylergonovine or carboprost as a second-line uterotonic depends primarily on provider preference and the presence of any medical contraindications. Methylergonovine must be avoided in patients at risk for hypertension; carboprost should be avoided in those with current reactive airway disease. If the second-line agent is unsuccessful in curbing the bleeding, the alternate agent is given. Carboprost may be re-administered as often as every 15 minutes; methylergonovine every 4 hours.

Further escalation in treatment involves medical and surgical measures, such as cytotec (misoprostol), intrauterine vasopressin injection, uterine massage, intrauterine balloon tamponade, occlusion of pelvic arteries, B-lynch sutures, or hysterectomy. In this study, patients will have the opportunity to receive one or both of the second-line agents, as well as all other standard measures for PPH management; however the choice of uterotonic that is given first will be randomized.

Describe how risks to subjects are minimized, for example, by using procedures which are consistent with sound research design and which do not unnecessarily expose subjects to risk or by using procedures already being performed on the subject for diagnostic or treatment purposes.

This study is designed as a double blinded, randomized study.

Several national and international guidelines have recommended both drugs as second-line uterotronics to treat PPH, but there is no evidence to specify which should be used first, or which might be more effective. Therefore, by giving the patients the opportunity to receive both drugs, any deviation from standard practice and risk to the patients will be minimized.

Describe explicitly the methods for ensuring the safety of subjects. Provide objective criteria for removing a subject from the study, for example, objective criteria for worsening disease/lack of improvement and/or unacceptable adverse events. The inclusion of objective drop criteria is especially important in studies designed with placebo control groups.

All participants will be under the direct care of an obstetric anesthesiologist, obstetrician, and a labor and delivery nurse throughout the course of the study. Standard care will be employed for every patient with the exception of the randomization of the order in which they receive their second-line uterotonic agents. At all times, providers' clinical assessment of the patient will be paramount in guiding decision-making. Providers will have full ability to exercise their best judgement in taking care of the patient. If this results in a decision to deviate from the study protocol, the patient will be cared for according to the providers' discretion. If the practice deviates from the study protocol, the patient will be withdrawn from the study thereafter.

Patients will be monitored carefully by their anesthesia and obstetric providers for any potential side-effects of the medications they receive in the study.

The principal investigator will additionally review all data collection and recruitment on every 5th patient recruited and immediately as needed if a concern arises. At the time of each review point, the principal investigator will review all forms and data entry to ensure completeness, accuracy, and adherence to the protocol. Any concern for adverse events will result in immediate review by the principal investigator with the study being temporarily halted, and the events will be reported to the IRB and the PHRC in accordance with the PHRC Policy on Unanticipated Problems Involving Risks to Subjects or Others, including Adverse Events. The principal investigator will be primarily responsible for deciding if the study needs to be stopped, but this can also be decided by any of the study co-investigators.

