Within the first 24 hours after delivery, but no sooner than the time of patient transfer from the labor and delivery floor to the postpartum unit, Between 2-4 hours postpartum and again between 18-24 hours postpartum, a blinded study investigator who is not involved in the subject's clinical care will interview the patient by phone (to avoid physical contact and minimize the risk for COVID-10 transmission) and record the information from the interview on the corresponding '2-4 Hr Interview Guide' or '18-24 Hr Interview Guide'. This will allow them to assess subjective side effects of the study medication such as G.I. upset, dizziness, shortness of breath, palpitations or chest pain. Non-English speaking patients will be interviewed in person with the assistance of an in-person interpreter from BWH Interpreter Services.

Subject randomization, patient MRN and the linked study ID number will be documented on a separate form in the secure electronic database, REDCap database by the unblinded principal investigator. This form will be visible only to the principal investigator. An unblinded study investigator (i.e. the principal investigator, or a research assistant, when one is hired in the future) with access to REDCap will be responsible for collecting and entering all primary and secondary outcomes from the Uterine Tone Score Intraop Data Collection sheet, the 2-4 Hour Interview Guide and the 18-24 Hour Interview Guide and Epic medical records (including side-effects of study medications) into REDCap. Subject randomization will be documented, on a separate form in the database to which only the principal investigator has access, in order to preserve the integrity of the data collection and entry.

The need for blood product administration and quantity of each component given within 24hrs after cesarean section will be recorded. In addition, the investigator will record any additional interventions performed to halt bleeding, such as Bakri balloon placement, B-Lynch sutures, uterine artery embolization or hysterectomy.

Total intravenous fluids given from start to conclusion of the delivery will be recorded. The use of vasopressors, uterotonic agents, anti-emetic agents will be recorded. Length of stay and any postoperative complications occurring during the hospital stay will be documented at the time of hospital discharge.

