## **VII. RISKS AND DISCOMFORTS**

Adverse reactions to methylergonovine include increased blood pressure, seizure, dizziness and headache, and nausea, vomiting, diarrhea and abdominal pain from uterine contractions. Rare effects include chest pain, myocardial infarction, coronary vasospasm, tachycardia, dyspnea, and hematuria. A large retrospective study of over 2 million parturients found no significantly increased risk of acute coronary syndrome or acute myocardial infarction after receiving methylergonovine. ACOG recommendations nonetheless state that methylergonovine should be avoided in patients with hypertension and cardiovascular disease.

The most common adverse reactions to carboprost include nausea, vomiting, diarrhea, as well as headache, myalgias, increased temperature and flushing. Due to its stimulation of smooth muscle contraction, modest increases in blood pressure may be seen, but these are generally clinically insignificant. Additionally, bronchospasm, abnormal ventilation-perfusion and hypoxia may occur, and may be particularly severe in patients susceptible to these complications. Carboprost is therefore contraindicated in patients with active asthma.

Patients with any contraindication to either of the study drugs will be excluded from participation in the study. Patients with a diagnosis of asthma will be interviewed to confirm if their asthma is active. Any patient who has used a bronchodilator within the past 24 months will be considered to have active asthma and will be excluded. If a patient carries a diagnosis of 'childhood asthma' and/or has not needed a bronchodilator for >24 months, they will be considered eligible to participate in the study. After enrollment, patients will be evaluated for all of the above side effects by a clinical investigator between at time of transfer to the postpartum floor and again between 18 to 24 hours after delivery. The obstetric 6-

week postpartum follow-up record will be reviewed by a clinical investigator to screen for thrombotic events or other side effects.

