**Please DO NOT access the patient's record prior to completing this form!**

Did the patient have any of the following before transfer to the postpartum floor?

	YES	NO
Nausea?		
Vomiting?		
Diarrhea?		
Shortness of Breath?		
Headache?		
Blurred Vision?		
Severe Anxiety?		
Chest Pain?		
Abnormal Sweating?		

Patient Name: \_\_\_\_\_

MRN: \_\_\_\_\_

Study Number: \_\_\_\_\_

Date/Time of Interview: \_\_\_\_\_

Questions or Concerns:

[name]  
e: [contact]  
pg: [name]

Page 62 of 99

**2-4 HR POSTPARTUM  
BLINDED INTERVIEW GUIDE  
SECOND-LINE UTEROTONICS in PPH STUDY**

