**Please DO NOT access the patient's record prior to completing this form!**

Did the patient have any of the following before transfer to the postpartum floor?

	YES	NO
Nausea?		
Vomiting?		
Diarrhea?		
Shortness of Breath?		
Headache?		
Blurred Vision?		
Severe Anxiety?		
Chest Pain?		
Abnormal Sweating?		

Patient Name: \_\_\_\_\_

MRN: \_\_\_\_\_

Study Number: \_\_\_\_\_

Date/Time of Interview: \_\_\_\_\_

Questions or Concerns:

[name]  
e: [contact]  
pg: [name]

Page 63 of 99

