At the end of the C/S, the anesthesiologist will return the Randomization sheet and the Uterine Tone Score Intraop Data Collection sheet in the previously sealed envelope to a folder where all paper documents for the study are temporarily stored in a locked room on the L&D floor. On each day of subject enrollment, the unblinded principal investigator will collect the envelope with the Randomization sheet and Uterine Tone Score Intraop Data Collection sheet and transfer it to a locked filing cabinet in a locked office to which only the principal investigator has access.

After the subject has recovered on the L&D floor and is ready for transfer to the postpartum floor, a blinded study co-investigator will interview the patient by phone (to limit physical contact, due to COVID-19 precautions)

using the '2-4 Hour Interview Guide'. At 18-24 hours postpartum, the subject will again be interviewed by phone by a blinded study co-investigator, using the '18-24 Hour Interview Guide'. Both postpartum interview guides will contain the same content, allowing for subjective adverse effects to be accurately assessed at 2 timepoints. (no later than 24 hours after delivery). This data will be documented on the 2-4 Hour and 18-24 Hour Interview Guides, to be retrieved by the principal investigator (who is not blinded) after the day of subject enrollment, then stored in the locked office, and ultimately entered into a secure electronic database, REDCap, by a blinded study investigator. This will allow them to assess for any subjective side effects of the study medication, as listed below (Secondary Endpoint #9).

An unblinded study investigator not involved in data collection and with access to REDCap will be responsible for collecting all primary and secondary outcomes (including side-effects of study medications) from the Uterine Tone Score Intraop Data Collection sheet, the Pre Transfer Interview Guide and Epic medical records onto the Second Line Uterotonics Data Collection Sheet and entering this information into REDCap. Subject randomization, patient MRN and the linked study ID number will be documented on a separate form in the REDCap database by the unblinded principal investigator, to preserve the integrity of the data collection and entry.

Study endpoints will be:

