All continuous secondary outcomes were initially assessed for the normality of residuals from a multivariable linear regression model with trial site and baseline uterine tone as covariates. Outcomes displaying normally distributed model residuals were analyzed using multivariable linear regression, with effect size presented as adjusted difference in means with 95% CI. Outcomes with all non-zero values that displayed skewed linear regression model residuals were natural log-transformed and analyzed using multivariable linear regression, with effect size presented as adjusted ratio of geometric means with 95% CI. Outcomes containing at least one zero value that presented skewed linear regression model residuals were compared between groups using multivariable quantile regression, with effect size presented as adjusted difference in medians with 95% CI.

All binary outcomes were initially considered for comparison using multivariable logistic regression (for single measurements) or generalized estimating equations with a logit link (for repeated measurements) with trial site and baseline uterine tone as covariates. If the multivariable regression converged, effect size was presented as adjusted odds ratios with 95% CI. If the model did not converge due to low incidence, groups were compared using a Fisher's exact test and effect size presented as risk difference with exact 95% CI.

Time to receive second study drug was compared between groups using a multivariable Cox proportional hazards model, with effect size presented as adjusted hazard ratio with exact 95% CI. Complete-case analysis was performed for all secondary outcomes. All analyses were performed using SAS software version 9.4 (SAS Institute, Cary, NC).

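### Side-effect endpoint #9 names 11 symptoms within 2 hours postpartum, but the forms shown solicit nine, over a period that has no start and ends at transfer

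*Protocol*

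**What the plan says.** The Protocol Summary, Secondary Endpoints, item 9, reads "Medication side effects within 2 hrs postpartum: nausea, vomiting or diarrhea, abdominal pain, shortness of breath, headache, blurred vision, anxiety, chest pain, sweating, palpitations". The Detailed Protocol, Specific Aims, outcome 2(j), lists the same symptoms with the same 2-hour limit. The Detailed Protocol's own endpoint list in Section V mentions study drug side effects only in general terms, without a window, so the 2-hour definition rests on the first two places.

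The interviews are the stated means of measuring this endpoint. Of the interview data the Summary (Research Design and Methods) says: "This will allow them to assess for any subjective side effects of the study medication, as listed below (Secondary Endpoint #9". It adds: "Both postpartum interview guides will contain the same content, allowing for subjective adverse effects to be accurately assessed at 2 timepoints". The Detailed Protocol, Section V, says the interview assesses "side effects of the study medication such as G.I. upset, dizziness, shortness of breath, palpitations or chest pain".

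Two one-page guides are attached. Each opens with the same question, "Did the patient have any of the following before transfer to the postpartum floor", followed by the same nine yes/no rows, one of which is "Severe Anxiety". The SAP analyses binary outcomes by logistic regression when measured once, or by "generalized estimating equations with a logit link (for repeated measurements". It does not say which of these applies to the symptoms.

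**The concern.** The endpoint and the instrument meant to measure it differ in content and in time. A woman can pass through both interviews exactly as planned and never be asked about two of the listed symptoms. Her answers on the rest refer to a period other than the one in the endpoint.

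The two omitted symptoms matter for this comparison. Section VII of the Detailed Protocol and the methylergonovine label name abdominal pain as a reaction to that drug, and palpitations appear in both drug labels. The protocol treats the two drugs as equivalent choices, so tolerability could help decide between them.

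The second interview is presented as a second time point. If it asks the same question about the same past period, it yields a second recollection, and a repeated-measures model would describe it wrongly.

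**Working it through.** No sample size or power enters this point. The check sets the endpoint beside the forms.

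**1. Symptoms.** Inputs: Protocol Summary endpoint #9 and Specific Aims 2(j); both interview guides; the data collection sheet. Synonyms were mapped (dyspnea to shortness of breath, diaphoresis to sweating).

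| Endpoint symptom | Both guides | Data sheet |
|---|---|---|
| Nausea | yes | yes |
| Vomiting | yes | yes |
| Diarrhea | yes | yes |
| Abdominal pain | **no** | **no** |
| Shortness of breath | yes | yes |
| Headache | yes | yes |
| Blurred vision | yes | yes |
| Anxiety | severe only | severe only |
| Chest pain | yes | yes |
| Sweating | abnormal only | diaphoresis |
| Palpitations | **no** | **no** |

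- Listed: 11. With a field: 9. Without: 11 − 9 = 2, and 2/11 = 18%.
- Of the nine on the guides, two are worded more narrowly than the endpoint, so 9 − 2 = 7 match as defined.
- The intraoperative tone sheet has no symptom fields.
- Section V says the interview covers palpitations, so that omission does not look like a deliberate narrowing.

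**2. Period.** The endpoint runs from delivery to 2 hours. The guides give no start, and the end is transfer. Section V puts the first interview at 2-4 hours and not before transfer. The Summary's section on foreseeable risks says women stay several hours on the labor floor first. A yes on the guide can therefore come from any of three periods:

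- before delivery, which is outside the endpoint;
- from delivery to 2 hours, which is the endpoint;
- from 2 hours to transfer, which is outside the endpoint.

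If transfer is at 4 hours, the part after delivery is 4/2 = 2 times as long as the endpoint allows. No form shown records when a symptom began, so the middle period cannot be separated afterwards.

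**3. Second interview.** One attached guide is headed as the 2-4 hour form. The other lost its heading in the text available and is taken to be the 18-24 hour form, from its position and from the Summary's statement that the two have the same content. On that reading both ask about the period before transfer, and nothing after transfer is asked at either call. If the SAP's repeated-measures method were applied, two recollections of one period would enter as two occasions. The model allows for correlation between a woman's two answers, so the problem is one of interpretation: any difference between occasions would reflect recall, not the course of symptoms.

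**The case against.** **Other sources exist.** Section V and the Summary name the medical record as a source of side effects, and Section IX requires every adverse event to go on an Adverse Experience Form. That form and the database screens are not shown, some attachments are missing, and the data sheet's layout is damaged. A reader might infer that endpoint #9 cannot be computed at all. The documents do not support that: nine symptoms have fields and the other two may be charted. What stands is that neither symptom is put to every woman on any form shown, and the sheet to which the Summary sends chart data has no column for them.

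**Missing is not zero.** A reader might infer that the two symptoms would be reported as no events in either arm. Nothing in the documents codes an absent field as no, and the SAP applies complete-case analysis to every secondary outcome. The consequence is no analysis of those two symptoms, not a false null.

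**Pre-drug symptoms and power.** A reader might infer a calculable loss of power because the guides admit symptoms from before the injection. The endpoint's own clock starts at delivery and the study drug comes later, so symptoms between delivery and injection belong to the endpoint as defined. The forms add only what precedes delivery and what follows 2 hours, and the later cut-off could capture more true drug effect. The documents give neither symptom rates nor a power for this endpoint.

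**The SAP partly covers two answers.** Its repeated-measures method could take both interviews. But it does not tie that method to the symptoms, choose a contrast, or recognise that both answers concern one period.

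**Supporting text.** Section VII says "patients will be evaluated for all of the above side effects by a clinical investigator", but its list includes seizure and myocardial infarction. It reads as general safety surveillance and is weak evidence of what the interview should contain.

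**Conclusion.** The mismatch is real and limited. As planned, 2 of 11 listed symptoms are not solicited on any form shown and two more are worded more narrowly. All nine that are asked cover an open-ended period before transfer instead of the first 2 hours. The interview answers cannot recover the 2-hour window.

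That the second interview adds no new period depends on the unheaded guide being the 18-24 hour form, which the Summary's own description supports. The conclusion about missing fields assumes that the forms shown are the ones in use.

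The primary endpoint and the other secondary endpoints are untouched, and the interviewer is blinded. The point is still worth acting on: left as it is, the trial would report a patient-reported side-effect endpoint that differs in content and timing from the one it defined.

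**What to change.** **If women are still being interviewed:**

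- Add abdominal pain and palpitations to both guides and to the data sheet.
- Make the 2-4 hour question match the endpoint, or restate the endpoint as running from delivery (or from the study injection) until transfer. Starting the clock at injection changes the endpoint and should be declared as such.
- Drop the qualifiers on anxiety and sweating, or write them into the endpoint.
- Give the 18-24 hour guide its own period, since the first interview.

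**If collection is finished**, which is likely because the SAP is written in the past tense and already counts patients with missing tone scores:

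- Report abdominal pain and palpitations as not solicited.
- Describe the other nine as patient-reported before transfer.
- Name the 2-4 hour answer as the one analysed. This settles which SAP method applies: single-measurement logistic regression. Where the second guide asked the identical question, use its answer only as a check on recall.

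**Cost.** Before completion: two rows on each of two one-page forms, two data-sheet columns, a reworded question on each guide, and an amendment. After completion: wording only. The downsides are that answers before and after a form change are not directly comparable, and that abdominal pain after cesarean is non-specific, so the added row will be hard to attribute to the drug.
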